5. STUDY SUBJECTS

5.1. General Consideration

Unless otherwise specified, all variables in Section 5 will be summarized for the MITT population for both Parts A and B.

5.2. Subject Disposition

For randomized subjects, the numbers and percentages of subjects who were randomized and dosed, discontinued study treatment in treatment period (including reasons for discontinuation), completed the study treatment, completed the study, and withdrew from the study in the treatment period (including reasons for withdrawal) will be summarized by treatment group.

Additionally, a listing of subjects who discontinued treatment and/or withdrew from study during the treatment period and the associated reasons for discontinuation/withdrawal will be provided. The number and percentage of subjects in each treatment group will be summarized for the MITT population.

5.3. Demography and Baseline Disease Characteristics – Part A and B

The following demographic and baseline characteristics will be summarized for the MITT population only – note that if the safety population differs from the MITT population (i.e. if not all subjects receive their randomized treatment) then the summaries will be repeated for the safety population only.

Part A

- Age categories (<40 years, ≥40 - <65 years, ≥65)
- Age (years)
- Sex (male/female)
- Ethnicity (Hispanic or Latino/not Hispanic or Latino/ Not reported due to confidentiality regulations)
- Race (American Indian or Alaska Native/Asian/Black or African American/ Native

CONFIDENTIAL

The information contained herein may not be used, disclosed, or published without the written consent of Biogen MA Inc.

Hawaiian or Other Pacific Islander/White/Not reported due to confidentiality regulations/Other)

- Height (cm)
- Weight (kg)
- Body Mass Index (kg/m²)
- Geographic region (United States, Asia, Latin America, Europe)
- CLE (Yes/No)
- CLE subtypes
 - ACLE
 - SCLE
 - DLE
 - CCLE other
 - Panniculitis
 - Chiblair
 - Tumidus

Additionally, the following baseline assessments will be summarized.

- Total active joint count
- Tender joint count
- Swollen joint count
- CLASI-A score
- [REDACTED]
- CLASI-A (≤ 10 , > 10)
- SLEDAI-2K score
- SLEDAI-2K (< 10 , ≥ 10)
- BILAG-2004 score
- BILAG-2004 grade (A, B, C, D, E)
- PGA of SLE (VAS) score

CONFIDENTIAL

The information contained herein may not be used, disclosed, or published without the written consent of Biogen MA Inc.

Part B

- Age categories (<40 years, ≥ 40 - <65 years, ≥ 65 years)
- Age (years)
- Sex (male/female)
- Ethnicity (Hispanic or Latino/not Hispanic or Latino/ Not reported due to confidentiality regulations)

CONFIDENTIAL

The information contained herein may not be used, disclosed, or published without the written consent of Biogen MA Inc.

- Race (American Indian or Alaska Native/Asian/Black or African American/ Native Hawaiian or Other Pacific Islander/White/Not reported due to confidentiality regulations/Other)
- Height (cm)
- Weight (kg)
- Body Mass Index (kg/m²)
- Geographic region (United States, Asia, Latin America, Europe)
- SLE (Yes/No)
- CLE subtypes
 - ACLE
 - SCLE
 - DLE
 - CCLE other
 - Panniculitis
 - Chiblair
 - Tumidus

Additionally, the following baseline assessments will be summarized.

- CLASI-A score
- CLASI-A ($\leq 10, > 10$)
- [REDACTED]
- SLEDAI-2K score
- SLEDAI-2K ($< 10, \geq 10$)
- PGA of SLE (VAS) score
- [REDACTED]
- [REDACTED]
- [REDACTED]

CONFIDENTIAL

The information contained herein may not be used, disclosed, or published without the written consent of Biogen MA Inc.

- [REDACTED]
- [REDACTED]
- [REDACTED]
- [REDACTED]
- [REDACTED]
- Concomitant medications
 - Antimalarials (Yes/No)
 - Corticosteroids (Yes/No)
 - Corticosteroids and antimalarials (Yes/No)
 - Azathioprine (Yes/No)
 - Methotrexate (Yes/No)
 - Mycophenolate (Yes/No)
 - Other Allowed Medications (Yes/No)
- [REDACTED]
- [REDACTED]

All baseline characteristics will also be presented in subject listings.

5.4. Prior Medications

Prior medications used for SLE and/or CLE

Previous medications used for the treatment of SLE and/or CLE(NSAIDS/Immunosuppressants/corticosteroids/antimalarials/others) will be summarized. A listing of previous medications used for the treatment of SLE and CLE will be presented, including the previous medication used, duration of treatment, used at screening (yes/no), and reasons for discontinuation if not using at screening (lack of efficacy/side effects/or other).

Prior medications used for non SLE/CLE

Previous medications used for the non SLE/CLE related treatment will be summarized.

CONFIDENTIAL

The information contained herein may not be used, disclosed, or published without the written consent of Biogen MA Inc.

 Biogen	Statistical Analysis Plan 230LE201	<V 2.0>
--	---	----------------------

A listing of previous medications used for the non SLE/CLE related treatment will be presented, including the previous medication used, duration of treatment, used at screening (yes/no), and reasons for discontinuation if not using at screening (lack of efficacy/side effects/or other).

5.5. Concomitant Therapies

A concomitant therapy (including medication or non-drug therapy) is defined as any therapy (other than the treatment) that is taken on or after the date/time of the randomized dose. This includes therapies that are started prior to the date/time of randomized dose if their use continues on or after Treatment Day 1.

In order to define concomitant for therapies with missing start or stop date, the following additional criteria are defined:

- if both the start and stop dates of a therapy are missing, that therapy is considered concomitant;
- if the start date of a therapy is missing and the stop date of that therapy falls on or after the date of randomized dose, that therapy is considered concomitant;
- if the start date of a therapy is prior to the date/time of randomized dose and the stop date of that therapy is missing, that therapy is considered concomitant;
- if the start and the stop dates of a therapy is prior to the date/time of randomized dose, that therapy is considered prior.

All concomitant medications will be coded using the World Health Organization (WHO) medication dictionary (March 2017 Version). All concomitant non-drug treatments will be coded by Medical Dictionary for Regulatory Activities (MedDRA) preferred term (Version 21.1 or the most updated version at data base lock).

Concomitant medications will be summarized separately for medications used to treat SLE, medications used to treat CLE, and medications used for other indications. The number and

CONFIDENTIAL

The information contained herein may not be used, disclosed, or published without the written consent of Biogen MA Inc.

percentage of subjects taking each medication as collected in the eCRF will be summarized. All concomitant medications will be presented in the data listings.

5.6. Treatment Exposure and Compliance

The duration of treatment exposure during the treatment period will be based on the number of days between the date of first dose and the date of the last dose + 28 days. Each dose should be administered in the clinic during the randomization visit and recorded in the electronic case report form (eCRF).

The number and percentage of subjects in each of the following cumulative durations of exposure categories will be summarized for each part as follows:

Part A

At least 2, 4, 8, 12, 16, 20, weeks. In addition, days of exposure to the treatment will be summarized as a continuous variable with summary statistics.

Part B

at least 2, 4, 8, 12, weeks. In addition, days of exposure to the treatment will be summarized as a continuous variable with summary statistics.

BIIB059 treatment compliance during the treatment period will be assessed based on the drug administered as recorded in the eCRF. Overall compliance for each subject will be calculated and summarized for each treatment group. The compliance will be calculated using the following formula:

Percent Compliance = (actual number of doses administered)/(number of doses expected to be administered) *100

CONFIDENTIAL

The information contained herein may not be used, disclosed, or published without the written consent of Biogen MA Inc.

 Biogen	Statistical Analysis Plan 230LE201	<V 2.0>
--	---	----------------------

Note: For part B subjects, the “number of doses expected” in the formula above will depend on the protocol version to which the subject consents. For discontinued subjects, “number of doses expected” will be relative to the time of discontinuation.

5.7. Protocol Deviations

Protocol deviations identified during site monitoring will be captured in a Protocol Deviation Log and will be categorized as major or minor deviations based on protocol deviation classification prior to the final database lock. The major protocol deviations will be summarized and listed. The minor protocol deviations will also be listed. All summaries for protocol deviations will be presented only by treatment group.

Subjects that had at least one major protocol deviation that led to exclusion from the per-protocol population (see [Section 4.1](#)) will also be summarized.

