16.1. Efficacy

16.1.1. Analysis Population

For Part A and Part B, analysis of efficacy endpoints will be based on the intent-to-treat (ITT) population and the per-protocol (PP) population.

The ITT population is defined as all randomized subjects who received at least 1 dose of study treatment (whether or not the subjects adhered to the protocol). Subjects will be analyzed according to the study treatment to which they were randomized. Analysis of other non-safety endpoints (e.g., demographics) will also be based on the ITT population, unless otherwise specified in the SAP.

The PP population is defined as all subjects in the ITT population who do not meet the criteria for exclusion from analysis. The exclusion criteria will be defined prior to database lock for the final analysis.

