4.1. Definitions of Analysis Populations for Part A and Part B

Modified Intent-to-Treat (MITT) Population

The MITT population is defined as all randomized subjects who received at least 1 dose of study treatment (whether the subjects adhered to the protocol). Subjects will be analyzed according to the study treatment to which they were randomized. Analysis of other non-safety endpoints (e.g., demographics) will also be based on the MITT population.

Safety Population

The safety population will include the same subjects as defined for the MITT population. However, subjects will be analyzed by actual treatment received. If all subjects take the treatment as they were randomly assigned to, the safety population will be the same as the MITT population.

Per-Protocol (PP) Population

The per-protocol population will include the MITT subjects who do not have any major protocol deviations that could impact the efficacy assessments. Subjects will be analyzed by randomized treatment. Major deviations that could impact the efficacy assessments are:

Part A

- Actual treatment received is different from the planned treatment (e.g., patients received BIIB059 treatment while randomized to the placebo arm).
- Patients who have usage of disallowed concomitant therapy or SLE standard of care therapy that deviate from the protocol (specific rules for each concomitant therapy will be described in an addendum).
- Failing Inclusion/exclusion criteria that might potentially affect efficacy. The criteria listed in [Table 1](#) are considered not going to affect efficacy, thus they are not considered for per-protocol population.
- < 80% treatment compliance with study medication

CONFIDENTIAL

The information contained herein may not be used, disclosed, or published without the written consent of Biogen MA Inc.

- > 120% treatment compliance with study medication

Part B

- Actual treatment received is different from the planned treatment (e.g., patients received BIIB059 treatment while randomized to the placebo arm).
- Patients who have usage of disallowed concomitant therapy or SLE standard of care therapy that deviate from the protocol (specific rules for each concomitant therapy will be described in an addendum).
- Failing Inclusion/exclusion criteria that might potentially affect efficacy. The criteria listed in Table 1 are considered not going to affect efficacy, thus they are not considered for per-protocol population.

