5.8. Treatment Failure

For each part below, subjects who meet any of the following criteria will be considered as a treatment failure and considered as a non-responder in the efficacy analysis:

Part A

- Subjects who initiate or increase SLE standard of care therapy or other disallowed concomitant therapy (Table 8 of the latest protocol version) during the treatment period of the study.
- Subjects with corticosteroid dose increase above baseline during the treatment period except for what is allowed under rescue 1 during week 1 to 4.
- Subjects with more than 2 allowed rescues between week 1 to week 12.
- Subjects with any increase in corticosteroid during treatment period after week 20.

CONFIDENTIAL

The information contained herein may not be used, disclosed, or published without the written consent of Biogen MA Inc.

Part B

- Subjects who initiate disallowed concomitant therapy during treatment period of Part B (see Table 8 of the latest protocol version).
- Subjects who initiate or increase SLE/CLE standard of care therapy during the treatment period of the study.
- Subjects who initiate or increase corticosteroid dose above baseline during the treatment period of the study (oral or topical except those in Table 6 of the latest protocol version).

Note: Treatment failure subjects would be allowed to remain in the trial and receive investigational product, as applicable)

More detailed definition regarding specific concomitant therapy is described in and addendum to this SAP. For both parts, subjects' data considered as treatment failure will be handled as described in [Section 6.6](#).

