10.2. Interim Analysis 2 (IA2): End of Treatment Periods

After the last subjects complete the Double-Blind Treatment Periods for Part A (at Week 24) and Part B (at Week 16), an interim database lock will occur and an IA of efficacy and safety data will be conducted. All Investigators, study site personnel, and subjects will remain blinded to treatment assignments until after the end of the study. Members of the Biogen study team not in direct contact with the study sites will have access to the study data after all subjects complete all Week 24 assessments in Part A and all Week 16 assessments in Part B. Members of the Biogen study team who become unblinded to the data for this IA will have no further contact with study sites until after the final database lock.

Unblinding details will be provided in the unblinding plan.

The endpoints and analysis to be included in the IA1 and IA2 are listed in [Appendix B](#).

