Appendix B: Summary of Additional Interim Analyses

	Section of the SAP	Note:	Study Part
Subject disposition	5.2	IA1 and IA2, MITT population	Part A and B
Demography and baseline disease characteristics	5.3	IA1 and IA2, MITT population	Part A and B
Previous medications used for the treatment of SLE and/or CLE	5.4	IA1 and IA2	Part A and B
Treatment exposure	5.5	IA1 and IA2	Part A and B
Concomitant therapies	5.6	IA1 and IA2	Part A and B
Protocol Deviations	5.7	IA2: Summary of major protocol deviations	Part A and B
Primary endpoint: Primary analysis	6.2	IA1 and IA2: Part B: Model based and summary statistics over time Part A, IA1 Descriptive statistics by visit; IA2: Model based and summary statistics over time.	Part A and B
Secondary and additional efficacy endpoints	6.3, 6.4	Part A, IA1: Descriptive statistics by visit of the following endpoints- SRI-4, TJC, SJC, PGA of SLE (VAS), SLEDAI-2K, BILAG-2004, CLASI-A based endpoints, [REDACTED] [REDACTED] Part A, IA2: Model based and summary statistics by visit of the following endpoints- SRI-4, TJC, SJC, PGA of	Part A

CONFIDENTIAL

The information contained herein may not be used, disclosed, or published without the written consent of Biogen MA Inc.

		SLE (VAS), SLEDAI-2K, proportion of subjects with no new organ system affected, CLASI-A based endpoints, BILAG based severe flare; Descriptive statistics by visit for the following endpoints- BILAG-2004 score, [REDACTED] [REDACTED] [REDACTED]	
Secondary and additional efficacy endpoints	6.3, 6.4	Part B, IA1: Model based and summary statistic over time- CLASI-A based endpoints; Descriptive statistics by visit of the following endpoints- SLEDAI-2K, [REDACTED], Physicians Global assessment of SLE (VAS), [REDACTED]. Part B, IA2: Model based and summary statistic over time - CLASI-A based endpoints, SLEDAI-2K; Descriptive statistics by visit of the following endpoints - [REDACTED], PGA of SLE (VAS), [REDACTED] [REDACTED] [REDACTED]	Part B
Immunoglobulins (IgG, IgA, IgM) change from baseline by visit	7.3.2	Part A and B, IA1: Descriptive statistics by visit.	Part A and B

CONFIDENTIAL

The information contained herein may not be used, disclosed, or published without the written consent of Biogen MA Inc.

CONFIDENTIAL

The information contained herein may not be used, disclosed, or published without the written consent of Biogen MA Inc.

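### Deviation classification and per-protocol exclusions may stay open until the final lock, after part of the sponsor's study team has seen results by arm at IA2

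*SAP*

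**What the plan says.** **Deadline.** Under SAP 5.7, deviations found during site monitoring are logged and "categorized as major or minor deviations based on protocol deviation classification prior to the final database lock". Protocol 16.1.1 says of the per-protocol set: "The exclusion criteria will be defined prior to database lock for the final analysis".

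**Consequence of a major deviation.** SAP 4.1: "The per-protocol population will include the MITT subjects who do not have any major protocol deviations that could impact the efficacy assessments". It then lists the relevant kinds: wrong treatment received, disallowed or non-compliant concomitant therapy, eligibility failures outside Table 1, and compliance below 80% or above 120%. The therapy-by-therapy rules are left to an addendum with no stated date. SAP 5.8 also relies on an addendum for treatment failure: "More detailed definition regarding specific concomitant therapy is described in and addendum to this SAP".

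**IA2.** SAP 10.2 says that after the last subjects complete treatment in both parts "an interim database lock will occur and an IA of efficacy and safety data will be conducted". On access: "Members of the Biogen study team not in direct contact with the study sites will have access to the study data". Those unblinded "will have no further contact with study sites until after the final database lock". Protocol 9.3 and 16.7.2 say the same. Appendix B schedules the model-based primary analysis of both parts at IA2, and "IA2: Summary of major protocol deviations".

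**The concern.** A per-protocol analysis is useful as a check on the MITT result only if subjects are removed without knowledge of outcome by arm. Here the stated deadline for those removals falls after an unblinded look at every treatment-period efficacy endpoint. Someone who has seen IA2 could, within the written rules, upgrade or downgrade a deviation, or help settle a concomitant-therapy rule that decides who is excluded. Even if nobody did, the report could not show from the plan that the per-protocol set was fixed blind.

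At stake are the analyses in SAP 6.7:
- Part A: active joint count, percent change in CLASI-A, and SRI-4.
- Part B: percent change in CLASI-A, CLASI-50, and the 4-point and 7-point CLASI-A reductions.

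**Working it through.** The plan states no figure on this point, so the check is the order of events, plus one subtraction.

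**1. Order of events**

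| Step | Event | Source |
|---|---|---|
| 1 | Last Week 24 (Part A) and Week 16 (Part B) visits | Protocol 7.2.2, 7.3.2 |
| 2 | IA2 interim lock; part of the study team unblinded; primary models run | SAP 10.2, Appendix B |
| 3 | Safety follow-up completed | Protocol 7.2.3, 7.3.3 |
| 4 | Final database lock: stated limit for classification and per-protocol criteria | SAP 5.7, Protocol 16.1.1 |

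Step 4 follows step 2, so the stated limit is after unblinding.

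**2. Length of the window** (nominal study days)

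- Part A: final visit Day 253 − end of treatment Day 169 = 84 days.
- Part B: final visit Day 197 − end of treatment Day 113 = 84 days.

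This runs from the last treatment visit, not from unblinding. The window is therefore about 84 days, minus the time to clean and lock IA2, plus the time from last visit to final lock. The documents give neither lock time. IA2 also waits for both parts, so in the part that finishes first some or all follow-up may be over before anyone is unblinded.

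**3. Is there a firewall?**

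- IA1: SAP 10.1 bars the unblinded team from study conduct between the interim and final locks.
- IA2: SAP 10.2 bars contact with sites only. It says nothing about deviation review or per-protocol decisions.
- Both documents refer to an unblinding plan, which is not among them.

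**4. How much discretion remains?**

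| Per-protocol criterion (SAP 4.1) | Left open? |
|---|---|
| Wrong treatment received | Little |
| Compliance <80% or >120% | Little; computed under SAP 5.6 |
| Eligibility failures | Partly: Table 1 lists those to ignore; for the rest, someone must judge whether efficacy might be affected |
| Concomitant therapy | Yes: rules left to an undated addendum |
| Major versus minor classification | Yes: may be set or revised until the final lock |

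**5. What must already exist at IA2?** The summary of major deviations in Appendix B requires a classification by then, but SAP 5.7 does not stop it being revised. Appendix B as shown does not list the per-protocol analyses of SAP 6.7, so IA2 does not force the per-protocol list to be settled.

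**The case against.** The case for leaving the text alone has several parts.

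- **Few people are unblinded.** Only study team members without site contact gain access, and neither document says who classifies deviations. Monitoring is assigned to a contract research organisation (Protocol 19.1.1). This stands: decisions by unblinded staff are permitted, not planned.
- **The criteria are mostly fixed.** This stands for wrong treatment and compliance. It does not cover the three open items above.
- **The final lock may be only an outer limit,** kept so that follow-up deviations can be logged, with the real classification done for IA2. That is a reasonable reading, but the text does not bar later reclassification of treatment-period deviations.
- **The unblinding plan may contain a firewall.** It may. The protocol and SAP do not state one.
- **Per-protocol results are supportive.** Correct: SAP 6.1 makes MITT primary.

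Some stronger readings are tempting and are not supported. A reader might infer that treatment-failure decisions, and through them the primary result, are open to unblinded judgement. SAP 5.7 does not govern treatment failure. SAP 5.8 states the failure criteria itself, and the primary models run at IA2 need failure status applied under SAP 6.6. A reader might also infer that the whole sponsor team is unblinded, that the window is at least 12 weeks, or that the deadline was written before IA2 existed. The first contradicts SAP 10.2 and the second cannot be derived. The third cannot be checked, because the documents include neither the previous SAP nor a summary of the Version 5 protocol changes.

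**Conclusion.** The point holds in a limited form. The plan places the deadline for deviation classification and per-protocol criteria after an unblinded efficacy analysis, and nothing in either document freezes these decisions or reserves them for blinded staff. This is a stated deadline in the wrong place, not merely a missing detail.

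Its size is modest. The exposure lasts roughly the 84-day follow-up, less the time to lock IA2. The open discretion is the major/minor call, the judgement on some eligibility failures, and the concomitant-therapy rules. It reaches the supportive per-protocol analyses in both parts, not the primary MITT result through per-protocol membership.

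The conclusion assumes that the unblinding plan and the addendum, neither of which is available, do not already require a blinded freeze before IA2. If they do, the protocol and SAP need only say so.

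**What to change.** 1. In SAP 5.7 and Protocol 16.1.1, replace the final lock with the IA2 interim database lock as the deadline for classifying treatment-period deviations and fixing per-protocol membership.
2. Complete and sign off the concomitant-therapy addendum, including its treatment-failure definitions, and the per-protocol list while blinded, before the IA2 lock.
3. Have any deviation found later, including a treatment-period deviation discovered late, classified by staff who are still blinded, with the reason recorded. If the per-protocol list changes as a result, also report the analyses on the list frozen before IA2.

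The cost is wording plus earlier data review and cleaning. The extra work is small because Appendix B already requires major deviations to be summarised at IA2. The change must be made before that lock, since blinded sign-off by anyone unblinded at IA2 cannot be recovered afterwards.
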